9.2.6 Other Quality of Life Metrics

Patients will be asked to complete the FACT-HN and PRO-CTCAE quality of life forms (see Appendix). The FACT-HN will be assessed at baseline and at the 7-week (final week) of radiation. The PRO-CTCAE will be assessed at baseline and weekly with the PROMS scale.

The change in scores from baseline to the 6-week follow-up timepoint will be used for analysis.

All assessments are summarized in Table 1.

Table 1. Subject assessments.

| Parameters | Prior to Study Therapy | Weekly During Radiation Therapy | At First Follow-up (6-weeks post completion) |
|---|------------------------|---------------------------------|--|
| History and Physical ^a | X | | X |
| Performance status ^a | X | | X |
| Creatinine | X | | |
| PROMS Score ^b | X | X | X |
| HN-PSS Score ^a | X | X | X |
| FACT H&N ^b | X | | X |
| Weight | X | X | X |
| Daily opioid use (in morphine equivalents) ^a | X | X | X |
| Assess if feeding tube has been placed ^a | X | X | X |
| CTCAE and other adverse events ^a | X | X | X |
| PRO-CTCAE questionnaire ^b | X | X | X |

^a Physician or evaluator reported.

^b Patient reported.

REFERENCES

1. Starmer, H.M., et al., *Effect of gabapentin on swallowing during and after chemoradiation for oropharyngeal squamous cell cancer*. Dysphagia, 2014. **29**(3): p. 396-402.
2. Chaturvedi, A.K., et al., *Human papillomavirus and rising oropharyngeal cancer incidence in the United States*. Journal of Clinical Oncology, 2011. **29**(32): p. 4294-4301.
3. Marur, S. and A.A. Forastiere, *Head and neck cancer: changing epidemiology, diagnosis, and treatment*. Mayo Clin Proc, 2008. **83**(4): p. 489-501.
4. Pignon, J.-P., et al., *Meta-analysis of chemotherapy in head and neck cancer (MACH-NC): an update on 93 randomised trials and 17,346 patients*. Radiotherapy and Oncology, 2009. **92**(1): p. 4-14.
5. Trott, A., et al., *TAME: development of a new method for summarising adverse events of cancer treatment by the Radiation Therapy Oncology Group*. Lancet Oncol, 2007. **8**(7): p. 613-24.
6. Moslemi, D., et al., *Management of chemo/radiation-induced oral mucositis in patients with head and neck cancer: A review of the current literature*. Radiother Oncol, 2016. **120**(1): p. 13-20.

7. Epstein, J.B., et al., *Neuropathic and nociceptive pain in head and neck cancer patients receiving radiation therapy*. Head & neck oncology, 2009. **1**(1): p. 1.

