4.3 Protocol Treatment

[figure not shown]

Figure 1: Treatment schema, as described below.

4.3.1 Arm 1

Patients will receive a placebo along the same dosing schedule as the experimental arm (patients randomized to placebo will take the same number of capsules as those assigned to gabapentin).

This will also include standard supportive care for treatment-related pain and mucositis as needed during concurrent chemotherapy and radiation treatment, consisting of the following:

- Viscous lidocaine 2% oral solution
- Oral liquid or solid opioid medications- e.g., morphine, oxycodone. These will be introduced and titrated at the discretion of the treating physician when the patient-reported pain score is ≥ 4 on a 0-10 scale.

4.3.2 Arm 2

Gabapentin will be initiated at a dose of 300 mg to be taken at bedtime of the night prior to the first radiation treatment. During week 1, the dose will be 300 mg three times a day for a total daily dose of 900 mg. Starting week 2, the dose will be 600 mg taken 3 times per day for a total daily dose of 1800 mg. This will continue until one week after the end radiation treatment (week 8). Therapy will then be titrated down to 300 mg three times a day for 1 day, and then discontinued all together. The standard supporting care for treatment-related pain and mucositis described above will also be included.

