8. STUDY CALENDAR

The institutional review board (IRB) approval process is expected to be completed by March of 2017. The trial will start accrual of patients subsequently. Given the typical volume of patients treated at our institution, it is expected to take 1-1.5 years to accrue the required 60 patients to complete this study. Patients will be followed up until the first follow-up after completion of radiation treatment (6 weeks). The trial is expected to conclude January of 2019 with data analysis and reporting to take place subsequently.

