9. STATISTICAL CONSIDERATIONS

9.1 Study Endpoints/ Analysis Plan

9.1.1 Primary endpoint

The primary endpoint is change in quality of life and pain, as measured by the Patient-Reported Oral Mucositis Symptoms (PROMS) scale over the entire study period. This will be measured at baseline and weekly during clinic visits. Additional measurements will be obtained at 6-weeks (first follow-up) from the time of radiation treatment completion.

The PROMS scale consists of 10 questions on a visual analogue scale of 100-mm lines addressing oral functions affected by oral mucositis.[13] This questionnaire has been validated in patients undergoing radiation treatment for head and neck cancers and correlates well with clinician determined scores of mucositis.[14]

Repeated measures analysis of variance (ANOVA) will be used to determine if there was a significant difference between the mean PROMS scores of the two groups over the entire study period, and t-tests will be used to examine if there was a difference in the PROMS scores for the two groups at each week of the study period.

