9.1.2 Sample size/ Justification of Number of Subjects

Based on reported means and standard deviation of PROMS scores of patients undergoing radiation treatment, a total of 60 patients will be required to evaluate a 16% reduction in PROMS score at week 7 (final week) of radiation treatment, with $\alpha = 0.05$ and power = 80%. This assumes a 10% dropout rate.

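### Section 9.2.6 collects FACT-HN in week 7 of radiation, but the analysis sentence and Table 1 use the 6-week follow-up visit

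*Combined protocol and SAP*

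**What the plan says.** Section 9.2.6 and the table beneath it make three statements about when FACT-HN is measured.

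- Collection: "The FACT-HN will be assessed at baseline and at the 7-week (final week) of radiation".
- Analysis: "The change in scores from baseline to the 6-week follow-up timepoint will be used for analysis". This follows a paragraph that covers only FACT-HN and PRO-CTCAE and is not limited to either, so it applies to FACT-HN.
- Schedule: "All assessments are summarized in Table 1". The FACT-HN row of Table 1 is marked before study therapy and at first follow-up (6 weeks after completion). The cell for weekly assessments during radiation is blank.

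For the companion instrument the text reads: "The PRO-CTCAE will be assessed at baseline and weekly with the PROMS scale". Section 9.1.1 places PROMS at baseline and weekly, and adds: "Additional measurements will be obtained at 6-weeks (first follow-up) from the time of radiation treatment completion".

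**The concern.** The visit in the collection sentence is not the visit that is analysed. A coordinator who schedules from that sentence obtains a baseline and a week-7 form, and has no post-baseline score for the planned change. A coordinator who schedules from Table 1 obtains the analysed score but not the week-7 form that the text asks for. Neither form can be completed retrospectively.

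The two visits also answer different questions. Under section 4.3.2, study drug continues until one week after radiation ends (week 8) and is then stepped down over one day. Week 7 is therefore on radiation and on study drug, while the 6-week follow-up falls about five weeks after study drug stops (13 − 8 = 5). If both scores were collected at some visits and only one at others, the choice of score would affect what the FACT-HN result means, so it should be settled in advance.

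**Working it through.** The documents give no figure to reproduce for this point, and no sample size, power or alpha enters it. The check compares the stated visits.

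**1. FACT-HN visits by source**

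| Source | Baseline | Week 7 of radiation | 6-week follow-up |
|---|---|---|---|
| 9.2.6, collection sentence | yes | yes | not named |
| 9.2.6, analysis sentence | yes | not named | yes |
| Table 1 | yes | blank (weekly column) | yes |

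Post-baseline visits: collection sentence {week 7}; Table 1 {6-week follow-up}. The intersection is empty.

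**2. Could the two visits be the same?**

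- Section 9.1.2 calls week 7 the final week of radiation. Section 4.3.2 labels one week after the end of radiation as week 8, so radiation ends in week 8 − 1 = 7.
- Sections 8 and 9.1.1 and Table 1 count the follow-up 6 weeks from completion: 7 + 6 = week 13. The gap is 6 weeks.
- Check in days, assuming a Monday start, 5 fractions a week and no breaks: 35 fractions (section 4.2.1) take 7 weeks, so the last falls on day 6 × 7 + 5 = 47. Follow-up is day 47 + 42 = 89. A week-7 visit on days 43 to 47 is 46 to 42 days earlier.
- Widest stated window: section 4.4 mentions follow-up at 2 ± 1 months. If that runs from completion (an assumption), 1 to 3 months is 30.4 to 91.3 days, or 4.3 to 13.0 weeks. Adding 7 gives weeks 11.3 to 20.0. Week 7 lies outside.

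A week-7 form cannot serve as the follow-up score.

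**3. Does another section settle it?**

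- Section 1.1.1 names FACT-HN as part of an aim but gives no time.
- Section 4.4 has quality of life recorded at follow-up without naming an instrument, and allows a phone call in place of the visit.
- Section 8 gives the length of follow-up but no assessment grid.

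None of these reconciles the statements or ranks them.

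**4. Is the problem wider than FACT-HN?**

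- PROMS: the visits in 9.1.1 match Table 1.
- PSS-HN: 9.2.2 ties it to the primary endpoint's time points, which matches Table 1.
- PRO-CTCAE: 9.2.6 ties it to PROMS, and Table 1 marks all three columns.
- FACT-HN: the text names a visit that Table 1 leaves blank and omits the visit that Table 1 marks.

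That is 1 mismatch among 4 scored instruments. Section 1.1.1 lists 8 aims, and FACT-HN is part of 1, shared with PRO-CTCAE.

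**The case against.** The strongest reply is that the harm needs someone to read one sentence in isolation. The analysis sentence is in the next paragraph, and Table 1, the only visit-by-visit schedule, marks FACT-HN at follow-up. Two of three statements therefore agree and schedule the analysed score. Collection sentences elsewhere in section 9.2 are also incomplete: the PRO-CTCAE sentence does not name the 6-week visit outright, and 9.2.4 describes opioid assessment weekly during radiation while Table 1 adds baseline and follow-up. Week 7 may simply be an extra FACT-HN visit, left unmarked because Table 1 has no single-week column.

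Much of this stands. It makes the matter a wording conflict that creates a risk, and it shows that collecting at baseline, week 7 and 6 weeks would satisfy every statement. But no section states that reading, and a table introduced as a summary is not said to override the specific sentence above it.

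Two further objections deserve an answer. First, the documents do not prove which statement is the slip; section 9.1.2 sizes the trial on PROMS at week 7, so week 7 might be the intended FACT-HN comparison. That is a fair caution, and the sponsor should decide; 6 weeks is only the default that two of the three statements support. Second, naming an analysis model goes beyond the timing conflict, and 9.2.3 uses a Wilcoxon rank-sum test for its own change from baseline to 6 weeks. It is indeed a separate improvement, offered because the same sentence has to be edited anyway.

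**Conclusion.** The inconsistency is real. For FACT-HN, the one post-baseline visit in the collection sentence and the one in Table 1 and the analysis sentence do not overlap, and they lie 6 weeks apart on the protocol's own week count. That result needs no assumption beyond those week labels; the Monday start and the origin of the 4.4 window serve only as cross-checks.

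The consequence is conditional. The number of patients who might lack the analysed score cannot be derived, because it depends on which statement staff follow. It is confined to one secondary instrument. The choice of 6 weeks is legitimate and is not questioned. The correction should be made because it costs almost nothing and the possible loss is irreversible, but it does not threaten the trial's main conclusion.

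**What to change.** State the FACT-HN visits once, in the same terms in 9.2.6 and Table 1, and include the 6-week follow-up.

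- **Minimum wording:** *FACT-HN is completed at baseline and at first follow-up, 6 weeks after radiation ends.* Table 1 stays as it is.
- **If week 7 is also wanted:** *FACT-HN is completed at baseline, in week 7 of radiation, and at first follow-up, 6 weeks after radiation ends*, with a week-7-only mark in Table 1.

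Keep 6 weeks as the main FACT-HN comparison unless the sponsor states otherwise before unblinding, and label any week-7 comparison supportive.

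Complete the analysis sentence as well: *Change in FACT-HN from baseline to the 6-week follow-up is compared between arms in a linear model adjusted for baseline score and smoking stratum.* Both covariates are already collected, and smoking status is the stratification factor in section 4.5.1.

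Settle the visits before the first patient reaches week 7, so that no intended form is lost.

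**Cost.** The minimum version is two sentences and no extra forms. Its drawback is that no on-treatment FACT-HN remains, although weekly PROMS and PRO-CTCAE cover that period. Keeping week 7 costs one table mark and one extra form per patient, at most 60 forms, at a visit patients already attend. It adds burden in the final week of radiation and a second comparison to label.

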1.1 INTRODUCTION

1.1.1 Specific Aims

Strategies to minimize and mitigate external beam radiation therapy related mucositis and pain during the treatment of head and neck cancer remain limited. We hypothesize that gabapentin could be used to delay or reduce treatment-related pain, reliance on opioid medication, and improve the quality of life for these patients. The specific aims of this proposed study include the following:

- Evaluate the reduction or delay of mucositis related pain and morbidity with the use of gabapentin in patients with stage III or IV oropharyngeal squamous cell carcinoma undergoing definitive radiation with concurrent chemotherapy as part of their cancer management, compared to standard supportive side effect mitigation – using patient reported quality of life endpoints such as the Patient-Reported Oral Mucositis Symptoms (PROMS) scale.
- Assess morphine-equivalent opioid use in both treatment arms by collecting the patient's narcotic use in the previous 24-hour period at each weekly evaluation during radiation treatment.
- Report on change in Speech and swallow performance, as measured by the Performance Status Scale (PSS) for Head and Neck Cancer Patients.
- Evaluate changes in weight from baseline throughout treatment between the two arms.
- Calculate the proportion of patients who end up requiring a feeding tube by the end of treatment in both arms.
- Evaluate changes in patient-report quality of life using the Functional Assessment of Cancer Therapy Head & Neck (FACT-HN) and PRO-CTCAE metrics.
- Evaluate the adverse events associated with gabapentin.
- Evaluate the severity of radiation mucositis (grade 3-4, CTCAE, v. 4).

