4.2 Radiation Therapy

Radiation therapy, delivered concurrently with chemotherapy, will ultimately be determined by the treating radiation oncologist. The following guidelines should be followed:

4.2.1 Dose specifications:

Volumes and Lymph node levels should be defined as per the RTOG Head and Neck atlas <http://www.rtog.org/CoreLab/ContouringAtlases/HN.aspx>.

Definitive treatment (all primary treatment should be delivered with concurrent chemotherapy as per the treating medical oncologist) will be done with simultaneous integrated dosing (SID) in 35 fractions to a total dose of 70 Gy, 63 Gy and 56 Gy to the high-risk, intermediate-risk and low-risk CTVs, respectively.

4.2.2 Physical Factors:

All subjects will undergo radiographic imaging required for radiation treatment planning purposes using a CT scanner. Digitally reconstructed radiographs from the CT will simulate the patient geometry during radiation treatment, including the localization and immobilization methods. A virtual treatment planning procedure is used to design treatment fields mathematically from the CT images.

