| 50 | Eats only in presence of selected persons in selected places |
| 25 | Eats only at home in presence of selected persons |
| 0 | Always eats alone |
| 999 | Inpatient |

UNDERSTANDABILITY OF SPEECH /____/

- | | |
|-----|--|
| 100 | Always understandable |
| 75 | Understandable most of the time; occasional repetition necessary |
| 50 | Usually understandable; face-to-face contact necessary |
| 25 | Difficult to understand |
| 0 | Never understandable; may use written communication |

NCI CTCAE v4.0 mucositis oral

| Adverse event | Grade 1 | Grade 2 | Grade 3 | Grade 4 | Grade 5 |
|----------------|---|--|---|--|---------|
| Oral mucositis | Asymptomatic or mild symptoms; intervention not indicated | Moderate pain, not interfering with oral intake; modified diet indicated | Severe pain, interfering with oral intake | Life-threatening consequences; urgent intervention indicated | Death |

Oral mucositis is characterized by inflammation of the oral mucosa.

NCI CTCAE: National Cancer Institute Common Terminology Criteria for Adverse Events.

Reproduced from: Common Terminology Criteria for Adverse Events (CTCAE), Version 4.0, June 2010, National Institutes of Health, National Cancer Institute. Available at: http://evs.nci.nih.gov/ftp1/CTCAE/CTCAE_4.03_2010-06-14_QuickReference_5x7.pdf (Accessed October 22, 2013).

NCI PRO-CTCAE™ ITEMS

Item Library Version 1.0

As individuals go through treatment for their cancer they sometimes experience different symptoms and side effects. For each question, please check or mark an in the one box that best describes your experiences over the past 7 days...

1. In the last 7 days, what was the SEVERITY of your DIFFICULTY SWALLOWING at its WORST?

None Mild Moderate Severe Very severe

2. In the last 7 days, what was the SEVERITY of your MOUTH OR THROAT SORES at their WORST?

None Mild Moderate Severe Very severe

In the last 7 days, how much did MOUTH OR THROAT SORES INTERFERE with your usual or daily activities?

Not at all A little bit Somewhat Quite a bit Very much

3. In the last 7 days, what was the SEVERITY of SKIN CRACKING AT THE CORNERS OF YOUR MOUTH at its WORST?

None Mild Moderate Severe Very severe

4. In the last 7 days, what was the SEVERITY of your DIZZINESS at its WORST?

None Mild Moderate Severe Very severe

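### The weekly on-treatment PRO-CTCAE scores, including dizziness, have no planned between-arm analysis; the only stated analysis is change to a visit about 5 weeks after the last dose

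*Combined protocol and SAP*

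**What the plan says.** **Collection.** Section 9.2.6 states: "The PRO-CTCAE will be assessed at baseline and weekly with the PROMS scale". Table 1 marks PRO-CTCAE as patient reported and ticks it before therapy, weekly during radiation and at the 6-week follow-up.

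**Analysis.** For the two instruments in section 9.2.6, FACT-HN and PRO-CTCAE, the plan gives one rule: "The change in scores from baseline to the 6-week follow-up timepoint will be used for analysis". It names no test, item, score definition or between-arm contrast, and no use for the weekly values.

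**Content.** The PRO-CTCAE form in Appendix III covers swallowing, mouth or throat sores, cracking at the corners of the mouth, dizziness and pain, each over the past 7 days. The dizziness severity item reads: "In the last 7 days, what was the SEVERITY of your DIZZINESS at its WORST". Dizziness and sores also have an interference item. Pain has frequency, severity and interference items.

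**Dosing period.** Of the full dose, section 4.3.2 says: "This will continue until one week after the end radiation treatment (week 8". It goes on: "Therapy will then be titrated down to 300 mg three times a day for 1 day, and then discontinued all together".

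**Aims.** Section 1.1.1 includes "Evaluate the adverse events associated with gabapentin" and, as a separate aim, "Evaluate changes in patient-report quality of life using the Functional Assessment of Cancer Therapy Head & Neck (FACT-HN) and PRO-CTCAE metrics".

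**The concern.** The trial gives a drug during chemoradiation and asks patients each week, while they take it, about dizziness, pain and sores. The one analysis rule for those answers then takes the difference between a score before the drug starts and a score about five weeks after it stops. Followed as written, it describes recovery and cannot show how patients felt on gabapentin.

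The main loss is dizziness, which sections 1.2.2 and 4.3.3 both list as a gabapentin side effect. If more patients on gabapentin were dizzy in weeks 1 to 7 and the dizziness resolved after stopping, the planned PRO-CTCAE result would show no difference. The same applies to the PRO-CTCAE pain items, though PROMS covers part of that ground. The weekly forms also cost patients effort at a difficult time, and the plan gives their answers no stated use.

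**Working it through.** **1. When drug stops and when the score is taken (weeks from the start of radiation)**

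- Radiation length: section 4.2.1 delivers radiation "in 35 fractions to a total dose of 70 Gy". At 5 fractions per week (my assumption), 35 / 5 = 7 weeks. This agrees with sections 9.1.2 and 9.2.6, which call week 7 the final week.
- End of full dose: 7 + 1 = week 8, which reproduces the plan's own figure.
- End of the one-day taper: 8 + 1/7 = week 8.14.
- Follow-up visit: 7 + 6 = week 13.
- Gap from last dose to visit: 13 − 8.14 = 4.86 weeks, or 42 − 8 = 34 days.
- Start of the 7-day recall: 42 − 7 = day 35 after radiation, which is 35 − 8 = 27 days after the last dose.

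Section 7.1 gives a half-life of 5 to 7 hours. In 27 days there are 27 × 24 = 648 hours, or 648 / 7 = 93 to 648 / 5 = 130 half-lives. The recall period is drug-free.

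**2. The other follow-up window**

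Section 4.4 gives 6 weeks and also 2 ± 1 months. Take a month as 30.4 days and count from the end of radiation (my assumption):

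| Visit | Days after radiation | Gap from last dose | Recall starts, days after last dose |
|---|---|---|---|
| 1 month | 30.4 | 22.4 days (3.2 weeks) | 15.4 |
| 6 weeks | 42 | 34 days (4.9 weeks) | 27 |
| 3 months | 91.3 | 83.3 days (11.9 weeks) | 76.3 |

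Even the earliest visit has a recall period wholly off drug.

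**3. What is left unused**

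About 7 weekly forms × 60 patients = 420 forms before dropout. With 1:1 allocation, about 210 come from the gabapentin arm. The stated rule uses none of the 420.

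**4. Which on-treatment symptoms are compared between arms elsewhere**

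| Symptom | Planned on-treatment comparison between arms |
|---|---|
| Mouth and throat pain | Yes, within the PROMS score: repeated measures ANOVA and weekly t-tests (9.1.1) |
| Effect of sores on speaking, eating, drinking, swallowing | Yes, within the PROMS score (items 2 to 9) |
| Grade 3-4 mucositis, clinician graded | Yes, Fisher's exact test (9.2.5) |
| Pain frequency, worst severity and interference (PRO-CTCAE) | None stated |
| Sore severity and interference (PRO-CTCAE) | None stated |
| Dizziness, patient reported | None stated |
| Dizziness, as an adverse event | Assessed weekly (4.3.3); gabapentin-related events are reported (9.2.5), with no contrast stated |

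**5. What an on-treatment comparison could show at this sample size**

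The target of 60 cannot be reproduced, because the PROMS mean and SD are not given; nothing above depends on it. With 10% dropout, 60 × 0.9 = 54 patients, or 27 per arm. At two-sided 0.05 and 80% power, the detectable standardised difference is (1.96 + 0.84) × √(2/27) = 0.76.

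For any dizziness, using the normal approximation for two proportions and assumed rates that are not in the documents:

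| Placebo | Gabapentin | Power |
|---|---|---|
| 10% | 30% | 45% |
| 10% | 40% | 73% |
| 20% | 40% | 36% |
| 20% | 50% | 64% |

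At 10% against 30%, the 95% half-width for the difference is 1.96 × √[(0.1 × 0.9 + 0.3 × 0.7)/27] = 1.96 × 0.105 = 0.21, or 21 percentage points. The analysis would therefore estimate a difference, not confirm one.

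**The case against.** **The plan already tests on-treatment pain and sores.** A reader might infer that patient-reported pain and mouth sores on gabapentin are never compared between arms. The documents do not support that. PROMS is the primary endpoint, is compared at each week and over the whole period, starts with mouth pain defined to include the throat, and ties items 2 to 9 to mouth sores. The pain aim in section 1.1.1 names PROMS as its example instrument. This objection stands in full. What PROMS leaves out is dizziness, general pain frequency and interference, and sore severity and interference as items.

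**Tolerability has its own route.** Side effects are assessed weekly, adverse events are ticked weekly in Table 1, and section 9.2.5 reports those related to gabapentin. Nothing says tolerability will be judged from the 6-week PRO-CTCAE change, so it would go too far to infer that the plan forces a reassuring safety conclusion. But this route is evaluator reported, and no between-arm contrast is stated for it. It does not replace a comparison of what patients themselves report.

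**PRO-CTCAE may not be the only patient report of a gabapentin side effect.** A reader might infer that it is. That cannot be checked: fatigue and somnolence are also listed side effects, and the FACT-HN items are not shown. The point is therefore confined to dizziness and to the instruments reproduced in Appendix III.

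**The rule does not exclude other analyses.** True, and it might even be meant for FACT-HN alone. On that reading PRO-CTCAE has no stated analysis at all, so the gap remains.

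**More items mean more comparisons with little power.** Also true. It bears on how the results are labelled, and is no reason to leave the weekly data without an analysis.

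**Conclusion.** The point holds in this form: the weekly PRO-CTCAE items have no planned on-treatment comparison between arms, and the one stated analysis uses a visit about 34 days after the last dose, with a recall that covers no time on drug. The range is about 3 to 12 weeks under the looser follow-up window, and the conclusion is the same throughout. About 7 forms per patient are left unused. The consequence is clearest for patient-reported dizziness. For pain and sores it is limited to aspects that PROMS does not measure.

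This is a gap in a secondary analysis. It does not affect the primary endpoint or the sample size. It rests on 5 fractions per week, on drug stopping as section 4.3.2 schedules, and on counting follow-up from the end of radiation.

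**What to change.** In section 9.2.6, replace the single analysis sentence for PRO-CTCAE with three elements.

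1. **On-treatment comparison.** For each item, compare the arms on the worst post-baseline score during radiation, adjusted for the baseline score and the smoking stratum, for example with an ordinal model. A longitudinal ordinal model over weeks 1 to 7 is an acceptable alternative; choose one before unblinding. Put dizziness first, with pain and mouth or throat sores as supportive items. Include patients who reduce or stop study drug, in line with the intent-to-treat follow-up in sections 4.3.4 and 5.1.1, and report the number of completed forms per arm, because a worst score depends on it.
2. **Labelling.** Call these analyses secondary and estimation-focused. Report effect estimates with 95% confidence intervals, and do not read a non-significant result as evidence of no excess dizziness.
3. **Recovery phase.** Keep the change from baseline to the 6-week follow-up as a separate result labelled as recovery after stopping study drug. Reconcile the two follow-up times in section 4.4, so that this time point is defined once.

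The cost is a paragraph of analysis text and a few tables. All the data are already scheduled, and no patients are added. The downside is a few more descriptive secondary comparisons, with the limited power shown above.

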4.5 Assignment of interventions

4.5.1 Allocation sequence generation

Separate randomization lists will be produced by a statistician for current smokers as well as for former/ non-smokers with a goal of 1:1 allocation to both treatment arms.

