9.2.4 Opioid Use

Patients with at least 1 reported administration of opioid analgesic will be considered to have received opioid analgesics. The total dose of opioid analgesics will be the sum of all opioid analgesic administrations that have been converted to morphine equivalents (see Appendix II). Use of opioid analgesics will be assessed for a 24-hour period before completing the assessment weekly during radiation. The relationship between analgesic use and treatment-related pain will be evaluated using the general linear model with (at minimum) stratification, treatment arm, and compliance.

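### Section 9.2.6 makes change from baseline the FACT-HN analysis variable and specifies no adjustment for baseline score or smoking stratum; adding both would usually gain precision at almost no cost

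*Combined protocol and SAP*

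**What the plan says.** Section 9.2.6 introduces FACT-HN and PRO-CTCAE together and gives one sentence on analysis: "The change in scores from baseline to the 6-week follow-up timepoint will be used for analysis". As placed, it appears to cover both instruments. It names an analysis variable but no test, model, covariate or significance level.

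Section 4.5.1 sets the randomisation factor: "Separate randomization lists will be produced by a statistician for current smokers as well as for former/ non-smokers", with 1:1 allocation as the goal. Only section 9.2.4 names that factor as a model term. It plans, for the relation between analgesic use and pain, a "general linear model with (at minimum) stratification, treatment arm, and compliance". The nearest parallel to the FACT-HN analysis is weight in section 9.2.3, where percent change is compared between arms by an unadjusted rank test.

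The timing of FACT-HN is inconsistent within section 9.2.6. The text says: "The FACT-HN will be assessed at baseline and at the 7-week (final week) of radiation". Table 1 marks FACT-HN before therapy and at the 6-week follow-up, and not during radiation. The analysis sentence agrees with Table 1.

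**The concern.** A change score fixes the slope of follow-up on baseline at 1. If the true slope is lower, the comparison carries avoidable noise, and a chance difference between arms at baseline is over-corrected. Here seven weeks of chemoradiation lie between baseline and follow-up, so a modest correlation is plausible. The text and Table 1, each taken alone, give a single post-baseline FACT-HN score per patient, so repeated measurement would not recover the lost precision.

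What is at stake is the precision of a secondary quality-of-life comparison with about 27 patients per arm. In addition, the choice between a t-test on change, a rank test and an adjusted model is left open. Section 4.5.4 has the study unblinded after the last primary-endpoint visit, and nothing fixes the FACT-HN model before then.

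**Working it through.** **Inputs from the plan.** Section 9.1.2 gives 60 patients, alpha 0.05, 80% power and 10% dropout, all for PROMS at week 7. Section 4.5.1 gives 1:1 allocation. For FACT-HN the plan gives no SD, correlation, effect or power.

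**The plan's own figure.** 60 × 0.9 = 54 evaluable, or 27 per arm, and 54/0.9 = 60, so the dropout step is consistent. Two-sided (sidedness is not stated), 27 per arm with 80% power implies a standardised effect of (1.960 + 0.842) × √(2/27) = 0.76. A 16% reduction then needs an SD of 0.16/0.76 = 21% of the control mean. The PROMS mean and SD are not given, so 60 can be neither confirmed nor refuted. Only the 27 per arm is carried forward.

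**Assumptions.** Baseline SD 1, follow-up SD k, correlation ρ; two-sided alpha 0.05; change-score power of 80% for FACT-HN.

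**Variances per patient.**

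- Change score: 1 + k² − 2ρk
- ANCOVA: k²(1 − ρ²)
- Difference: (1 − ρk)²

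The difference is never negative and is zero only when the true slope ρk equals 1. With equal SDs the ratio R of ANCOVA to change-score variance reduces to (1 + ρ)/2.

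**Power with baseline adjustment** = Φ(2.802/√R − 1.960).

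| k | ρ | Change variance | ANCOVA variance | R | Power, % | Gain, points |
|---|---|---|---|---|---|---|
| 1 | 0.3 | 1.400 | 0.910 | 0.65 | 93.5 | 13.5 |
| 1 | 0.5 | 1.000 | 0.750 | 0.75 | 89.9 | 9.9 |
| 1 | 0.7 | 0.600 | 0.510 | 0.85 | 86.0 | 6.0 |
| 1.5 | 0.3 | 2.350 | 2.048 | 0.871 | 85.1 | 5.1 |
| 1.5 | 0.5 | 1.750 | 1.688 | 0.964 | 81.4 | 1.4 |
| 1.5 | 0.7 | 1.150 | 1.148 | 0.998 | 80.1 | 0.1 |

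In the last row the true slope is 0.7 × 1.5 = 1.05, close to the value that the change score assumes, so there is almost nothing to gain.

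**Small-sample check.** The formula ignores the cost of estimating the slope. A simulation with equal SDs (8,000 runs per correlation, t-test on change against ANCOVA with arm and baseline) gave 80.7% against 93.1% at ρ = 0.3, 80.6% against 89.4% at 0.5, and 80.1% against 84.9% at 0.7. The gains are about 12, 9 and 5 points. Formula and simulation together give about 5 to 14 points with equal SDs.

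**Other anchors, equal SDs, ρ from 0.7 to 0.3.** If the change score had 50% power, the gain would be 6.6 to 18.1 points; at 90% power, 4.0 to 8.0.

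**Baseline imbalance.** The standard error of the baseline difference is √(2/27) = 0.272 SD. With equal SDs, a one-standard-error imbalance moves the unadjusted change-score estimate by (1 − ρ) × 0.272, which is 0.19, 0.14 and 0.08 SD at ρ = 0.3, 0.5 and 0.7. An arm that starts higher has its change understated.

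**Smoking stratum.** Its prognostic strength for FACT-HN is not given, so no gain can be computed, and none is counted above.

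**The case against.** The strongest objection is that section 9.2.6 names a variable and not a model. A reader might infer that the plan has decided to leave out the baseline score and the stratum. The documents do not say that. A regression of change on arm, baseline score and stratum would satisfy the sentence, and it gives exactly the same treatment effect as ANCOVA of the follow-up score. Section 9.2.4 shows that the authors name model terms when they describe a model. This objection stands: the finding is that adjustment is not specified. The unadjusted weight comparison in section 9.2.3 makes an unadjusted reading natural but does not settle it.

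A reader might also infer that this trial loses a known 6 to 14 points of power. That does not stand either. The figure needs an assumed correlation, equal SDs and 80% power for FACT-HN, while the plan's 80% belongs to PROMS at week 7. The table shows most of the gain disappearing when the follow-up spread is 1.5 times the baseline spread.

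Nor would an unadjusted result be biased. Over repeated randomisation the change score is unbiased and keeps its type I error; the shift in the working is conditional on an imbalance actually observed.

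Finally, ANCOVA is not better in every case. Estimating the slope adds about 1/(54 − 4) = 2% to the variance, so if the true slope is near 1 the change score is marginally more precise.

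**Conclusion.** The point holds as an efficiency recommendation, not as an error. Section 9.2.6 fixes change from baseline as the FACT-HN variable (and apparently the PRO-CTCAE variable) and specifies neither the baseline score nor the smoking stratum as a covariate, although both are already collected. An unadjusted analysis would be valid but generally less precise, and it would be open to a shift from observed imbalance.

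The size cannot be fixed from the documents. The illustrative gain of 5 to 14 points rests on equal SDs; with a follow-up SD 1.5 times the baseline SD it is 0 to 5. Both ranges assume 80% power for the change score. The smoking stratum may add to this by an unknown amount.

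FACT-HN is a secondary endpoint with no stated power, so the effect on the trial's main conclusion is limited. The timing conflict is the more basic defect: if FACT-HN is collected only when the text says, the planned 6-week change cannot be computed. The case for adjustment survives that conflict, because each version gives one baseline and one post-baseline score.

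**What to change.** First reconcile the FACT-HN assessment time across the text of section 9.2.6, its analysis sentence and Table 1. Then replace the analysis sentence for FACT-HN with:

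> The post-baseline FACT-HN score at the reconciled time will be compared between arms by ANCOVA with treatment arm, baseline FACT-HN score and smoking stratum as terms, and the adjusted mean difference with 95% CI will be reported; mean change will be descriptive.

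The section should also say whether the change-score sentence is meant for PRO-CTCAE and, if so, which model applies. The changes should be made before unblinding.

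The cost is a short text change with no new data, two degrees of freedom, and a negligible loss of precision if the true baseline slope is near 1. In practice this is a free improvement.
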